UNS			X	X	X	X	X		X		

ADA=anti-drug antibody; C=cycle; D/d=day; DNA=deoxyribonucleic acid; h=hour(s); H2H=head-to-head; min=minutes; PBMCs=peripheral blood mononuclear cells; PK=pharmacokinetic(s); RNA=ribonucleic acid; seq=sequencing; UNS=unscheduled.

1. After flush.
2. ADA and biomarker samples in even cycles only.
3. Cycle 2 only.
4. For RRMM: collect sample at C4D1 only. Testing at these time points is for immunophenotyping only.
5. Collect if clinically feasible.

**Table 1-14 Schedule for PK, Biomarker/Pharmacodynamic, and Immunogenicity Sampling – Daratumumab SC-Treated Subjects – Expansion Part B (Randomized H2H)**

Cycle (28-day cycles)	Day (Window)	Time Point (Window)	PK	ADA	Cyto- kines	Comple- ment	Immuno- pheno- typing	Pro- teomics	Explora- tory PBMCs	DNA- seq control sample (saliva)	Bone Marrow for Immuno- phenotyping and DNA/ RNA seq
Screening	Day -21 to Day -1			X						X	X
Cycle 1	Day 1	Predose (-30 min)	X	X	X	X	X	X	X		
		End of injection +4 h (±30 min)			X	X					
	Day 2	End of injection +24 h (±2 h)	X		X	X	X				
	Day 4	End of injection +72 h (±24 h)	X				X				
	Day 8	Predose (-30 min)	X		X	X	X	X			
	Day 15	Predose (-30 min)	X			X	X	X			
Cycle 2 to Cycle 6	Day 22	Predose (-30 min)	X	X		X	X	X			
	Day 1	Predose (-30 min)	X	X 			X	X	X		X 
	Day 8 (+2d)	Predose (-30 min)	X 								
	Day 15 (+2d)	Predose (-30 min)	X				X				
	Day 22 (+2d)	Predose (-30 min)	X 								
	Day 23	End of injection +24 h (±2 h)	X 								
Cycle 7 and Beyond	Day 25	End of injection +72 h (±24 h)	X 								
	Day 1 (+3d)	Predose (-30 min)	X	X 			X 		X 		
End of Treatment			X	X				X			X 
UNS			X	X	X	X	X		X		

ADA=anti-drug antibody; C=cycle; D/d=day; DNA=deoxyribonucleic acid; h=hour(s); H2H=head-to-head; min=minutes; PBMCs=peripheral blood mononuclear cells; PK=pharmacokinetic(s); RNA=ribonucleic acid; SC=subcutaneous; seq=sequencing; UNS=unscheduled.

1. ADA and biomarker samples in even cycles only.
2. Cycle 2 only.
3. Collect sample at C4D1 only. Testing at this time point is for immunophenotyping only.
4. Collect if clinically feasible.

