13. Extramedullary plasmacytomas should be assessed for all subjects with a history of plasmacytomas or if clinically indicated at Screening, by clinical examination or radiologic imaging. Results from radiologic plasmacytoma assessment performed within 42 days before C1D1 as routine follow up for subject's disease state may be used. Imaging methodology used for evaluation should be consistent across all visits. Irradiated or excised lesions will be considered not measurable, and will only be monitored for PD.

**Table 1-13 Schedule for PK, Biomarker/Pharmacodynamic, and Immunogenicity Sampling – GEN3014 IV-Treated Subjects – Expansion Part B (Randomized H2H)**

Cycle (28-day cycles)	Day (Window)	Time Point (Window)	PK	ADA	Cyto- kines	Comple- ment	Immuno- pheno- typing	Pro- teomics	Explora- tory PBMCs	DNA-seq control sample (saliva)	Bone Marrow for Immuno- phenotyping and DNA/ RNA seq
Screening	Day -21 to Day -1			X						X	X
Cycle 1	Day 1	Predose (-30 min)	X		X	X	X	X	X		
		End of infusion (+5 min)	X 								
		End of infusion +4 h (±30 min)			X	X					
	Day 2	Predose (-30 min) Day 2	X		X	X	X				
		End of Day 2 infusion (+5 min)	X 								
		End of Day 2 infusion +4 h (±30 min)	X		X	X					
	Day 3	End of Day 2 infusion +24 h (±2 h)	X		X	X	X		X		
	Day 5	End of Day 2 infusion +72 h (±24 h)	X				X				
	Day 8	Predose (-30 min)	X		X	X	X	X			
		End of infusion (+5 min)	X 								
	Day 15	Predose (-30 min)	X			X	X	X			
		End of infusion (+5 min)	X 								
	Day 22	Predose (-30 min)	X	X		X	X	X			
		End of infusion (+5 min)	X 								
Cycle 2 to Cycle 6	Day 1	Predose (-30 min)	X	X 			X	X	X		X 
		End of infusion (+5 min)	X 								
	Day 8 (+2d)	Predose (-30min)	X 								
	Day 15 (+2d)	Predose (-30min)	X				X				
	Day 22 (+2d)	Predose (-30min)	X 								
		End of infusion (+5 min)	X 								
		End of infusion +4 h (±30 min)	X 								
	Day 23	End of infusion +24 h (±2 h)	X 								
	Day 25	End of infusion +72 h (±24 h)	X 								

Cycle (28-day cycles)	Day (Window)	Time Point (Window)	PK	ADA	Cyto- kines	Comple- ment	Immuno- pheno- typing	Pro- teomics	Explora- tory PBMCs	DNA-seq control sample (saliva)	Bone Marrow for Immuno- phenotyping and DNA/ RNA seq
Cycle 7 and Beyond	Day 1 (+3d)	Predose (-30 min)	X	X 			X 		X 		
End of Treatment			X	X				X			X 

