**Table 3: Phase 2 Expansion Part B**

Objectives	Endpoints
Primary	

 
Compare overall response of GEN3014 IV vs daratumumab SC in anti-CD38 mAb-naïve RRMM subjects
 
	
 
ORR
 

Secondary	

 
Compare time dependency in PK between GEN3014 IV vs daratumumab SC
 
	
 
Ctrough levels of GEN3014 IV, or daratumumab SC, on Cycle 3 Day 1
 

 
Assess the anti-tumor activity of GEN3014 IV vs daratumumab SC
 
	
 
VGPR or better
 
CR or better
 
DOR
 
TTR
 
PFS
 
OS
 
Time to next therapy (TTNT)
 

 
Assess safety of GEN3014 IV vs daratumumab SC
 
	
 
Safety: Incidence and severity of AEs and SAEs, including changes in laboratory values, vital signs, ECGs
 
Immunogenicity: Anti-GEN3014 antibodies, anti-daratumumab antibodies, anti- rHuPH20 antibody
 

Exploratory	

 
Evaluate the pharmacodynamic profiles of GEN3014 and compare with those of daratumumab
 
	
 
Pharmacodynamic markers in blood and tumor samples, including frequencies of NK cells and other leukocyte subsets, and complement analyses
 

 
Assess potential biomarkers predictive of clinical response to GEN3014 and evaluate potential surrogacy with PFS and OS
 
	
 
CCI
 
Immune cell profiling
 
DNA mutation status and gene profile (RNA-seq)
 

 
Assess MRD status
 
	
 
Rate and duration of MRD-negative remission
 

 
Explore PK/pharmacodynamic relationship (PK/anti-tumor activity) and PK/safety
 
	
 
Dose concentration response (biomarkers and/or efficacy, safety) relationship
 

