#### **Immunophenotyping and complement analysis**

The immunophenotyping parameters are

- T-cells: CD3+, CD3+CD4+, CD3+CD8+
- NK-cells: CD3-CD56+/CD16+,
- B-cells: CD3-CD19+,
- monocytes: CD14+,
- complement analysis parameters: C2 and CH50.

The baseline value of the parameter will be presented by cohort, as well as the maximum absolute change and maximum absolute percentage change. For T-cells the maximum increase/expansion (and maximum percentage increase/expansion) from baseline will be presented. For NK-cells, B-cells, monocytes and complement analysis parameters, the maximum decrease/depletion (and maximum percentage decrease/depletion) will be presented.

Absolute and percentage changes from baseline in Cycle 1 will be presented in figures.

5.6.2.2

CCI

CCI

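### In Part B the maximum fall in C2 and CH50 is taken over 7 complement samples for GEN3014 but 5 for daratumumab, so it tends to look deeper for GEN3014 even if the drugs are identical

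*Protocol*

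**What the plan says.** Both documents list, as an exploratory Part B objective, to "Evaluate the pharmacodynamic profiles of GEN3014 and compare with those of daratumumab" (Protocol Table 3-3, SAP Table 3). Complement analyses are among the endpoints named for it.

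SAP 5.6.2.1 names C2 and CH50 as the complement parameters and sets the summary: "For NK-cells, B-cells, monocytes and complement analysis parameters, the maximum decrease/depletion (and maximum percentage decrease/depletion) will be presented". Presentation is by cohort. SAP section 3 calls each Part B arm of 40 a cohort, so here cohort means treatment arm. Nothing limits the maximum to sampling times that the arms share.

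Sampling is set by Protocol Table 1-13 (GEN3014) and Table 1-14 (daratumumab). The first GEN3014 dose is split over Days 1 and 2 and the first daratumumab dose is not (Protocol 4.1.4). GEN3014 subjects therefore have complement drawn around both half-doses, including at "End of Day 2 infusion +4 h (±30 min". In both tables the complement column is marked only in Cycle 1 and at unscheduled visits. SAP 5.1.2 keeps unscheduled visits out of summaries.

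**The concern.** A per-subject maximum rises with the number of noisy values it is taken over. If two arms have the same true profile but one is sampled more often, that arm shows the deeper average maximum. Complement is not scheduled again after Cycle 1, so later equal sampling never dilutes the imbalance.

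The direction matters because greater complement activity is the stated reason for testing GEN3014 against daratumumab (Protocol 2.2). A clinical readout of that mechanism should not lean toward the hypothesis because of a visit schedule. No p-value or decision rule is attached. What is at stake is how a side-by-side table of maximum C2 and CH50 depletion will be read.

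**Working it through.** The plan gives no figure for this comparison, so there is nothing to reproduce. The check counts samples and then sizes the effect.

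**Step 1. Scheduled post-baseline complement samples (Day 1 predose is baseline).**

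| Arm | Samples | Total |
|---|---|---|
| GEN3014, Table 1-13 | Day 1 +4 h; Day 2 predose; "End of Day 2 infusion +4 h (±30 min"; Day 3, "End of Day 2 infusion +24 h (±2 h"; predose Days 8, 15, 22 | 7 |
| Daratumumab, Table 1-14 | Day 1, "End of injection +4 h (±30 min"; Day 2, "End of injection +24 h (±2 h"; predose Days 8, 15, 22 | 5 |

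Through Day 3 the count is 4 against 2. From Day 8 it is 3 against 3.

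**Step 2. Cell samples, for contrast.** In Cycle 1 GEN3014 has 6 (Day 2 predose; Day 3; Day 5, "End of Day 2 infusion +72 h (±24 h"; Days 8, 15, 22). Daratumumab has 5 (Day 2; Day 4, "End of injection +72 h (±24 h"; Days 8, 15, 22). Both arms then have Days 1 and 15 of Cycles 2 to 6, which is 5 × 2 = 10 more. Through Cycle 6 the totals are 16 and 15.

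**Step 3. Expected maximum of k independent standard normal values.** E(M_k) = ∫ x · k · φ(x) · Φ(x)^(k−1) dx.

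- Complement, 7 against 5: 1.352 − 1.163 = 0.189 within-subject SD.
- Cells in Cycle 1, 6 against 5: 1.267 − 1.163 = 0.104 SD.
- Cells through Cycle 6, 16 against 15: 1.766 − 1.736 = 0.030 SD.

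If a share ρ of the variance lies between subjects, the complement excess in total-SD units is 0.189 × √(1 − ρ): 0.19 at ρ = 0, 0.13 at ρ = 0.5 and 0.08 at ρ = 0.8. In simulated trials of 40 against 40 with identical drugs, GEN3014 has the deeper mean maximum in 91%, 77% and 66% of trials respectively; a fair statistic gives 50%. An excess of more than 1.96 standard errors for GEN3014 appears in 26%, 11% and 6%, against about 2.5% if fair.

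**Step 4. Percentage scale.** Assume log-normal noise with σ² = ln(1 + CV²), one noisy baseline X₀ and no drug effect. The statistic is 100 × max over j of (1 − X_j/X₀). With independent noise, the mean maximum percentage decrease is:

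| Assumed CV | 7 samples | 5 samples | Excess (points) |
|---|---|---|---|
| 10% | 12.0 | 10.3 | 1.7 |
| 15% | 17.0 | 14.5 | 2.5 |
| 20% | 21.4 | 18.3 | 3.1 |
| 30% | 28.7 | 24.4 | 4.3 |

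Four of the GEN3014 samples fall within about 48 hours, so independence is generous. With serially correlated noise (assumed correlation time 1 to 7 days), the excess at CV 20% drops to about 0.9 to 2.0 points. At CV 10% with the longest correlation time it is about 0.5.

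**Step 5. Equal acute dip.** Suppose both drugs cause the same 20% fall in the early samples (4 for GEN3014, 2 for daratumumab), at CV 20%. With independent noise the means are 33.5 and 28.4, an excess of about 5 points. With serial correlation it is about 1.7 to 3.4 points.

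**Step 6. Matched times.** Over five samples in each arm, the expected maximum under the Step 3 model is 1.163 SD in both. The difference is 0, and GEN3014 looks deeper in about 50% of trials. With serial correlation at CV 20%, either five-time GEN3014 set described under the fix leaves a residual of less than 1 point, slightly against GEN3014.

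**The case against.** The strongest reply is that the plan makes no formal comparison of maxima. They are presented by cohort, with no difference, ratio or test. The objective is exploratory, Protocol 9.1 states no hypotheses, and Protocol 9.4.7 makes the daratumumab analyses optional. Time-resolved displays already exist: SAP 5.6.2.1 plots Cycle 1 changes from baseline, and Protocol 9.4.7 calls for marker-versus-time curves. A careful reader can compare like times there. All of this stands, and it limits the weight of the point. It does not make the table of maxima fair, since a descriptive table has no other safeguard.

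The extra samples also follow the dosing, because each half-dose has its own follow-up draws. That explains the imbalance but does not remove its effect on a maximum. Equal counts will not make a split IV dose fully comparable with an SC injection either; they remove only the part due to sample number.

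Two stronger readings are tempting. A reader might infer that cell depletion is biased in the same way. The SAP does not confine the cell maxima to Cycle 1, and through Cycle 6 the counts are 16 and 15, which makes the excess negligible. A cell maximum also depends on time on treatment, but the documents give no basis for sizing a difference between arms. A reader might also infer that GEN3014 is bound to show the deeper depletion. The bias is in expectation only: with identical drugs, daratumumab would still look deeper in roughly 9% to 34% of trials under the Step 3 model.

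**Conclusion.** The point holds for C2 and CH50 in Part B. The counts of 7 and 5 and the absence of a matched-time rule come directly from the documents, and the direction of the lean follows from them. Its size rests on assumptions, because the documents give no CV, no serial correlation and no expected complement dip. With no drug effect and an assumed CV of 10% to 30%, the spurious excess is about 0.5 to 4.3 percentage points. Values near the top need independent noise. An equal acute dip in both arms makes it larger.

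This is a modest flaw in one exploratory, descriptive summary. The documents do not support reading it as a threat to the primary ORR comparison, as a material problem for cell subsets, or as proof that any observed complement difference is an artefact. It is worth correcting because it favours the trial's mechanistic hypothesis and costs very little to remove.

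**What to change.** Add a paragraph to SAP 5.6.2.1. For Expansion Part B, derive the maximum change and maximum percentage change in C2 and CH50 over five nominal times matched between arms: about 4 h and about 24 h after the first dose, plus predose Days 8, 15 and 22.

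For daratumumab the early pair is Day 1 +4 h and Day 2. For GEN3014, fix one of two pairs before data are reviewed:

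- after the Day 1 infusion: Day 1 +4 h and Day 2 predose, which captures first exposure but only half the dose; or
- after the Day 2 infusion: Day 2 +4 h and Day 3, which captures the full first dose but not first exposure.

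Either is much closer to fair than the present rule, so the choice matters less than making it in advance. Show the remaining GEN3014 samples only in listings and by-time figures.

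The cost is one SAP paragraph, with no new sample or visit. Two GEN3014 complement samples drop out of the between-arm maximum.

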**Table 1-15 Minimal Residual Disease CCI Evaluation Schedule – Subjects with RRMM – Expansion Part B (Randomized H2H)**

Screening or Treatment Cycle (28 days per cycle)	Screening	Post-treatment Collection
Day (window)	Day -21 to Day -1	±1 month
Bone marrow aspirate for MRD	X	At CR/sCR, and at 6, 12, 18, 24, and 30 months post C1D1 for subjects who achieve CR/sCR and remain on trial
Whole blood MRD CCI	X	At CR/sCR, and at 6, 12, 18, 24, and 30 months post C1D1 for subjects who achieve CR/sCR and remain on trial

C=cycle; CR=complete remission; CCI; D/d=day; H2H=head-to-head; MRD=minimal residual disease; RRMM=relapsed or refractory multiple myeloma; sCR=stringent complete response.

## 2 INTRODUCTION

### 2.1 Background

#### 2.1.1 Overview of Diseases

##### 2.1.1.1 *Multiple Myeloma*

Multiple myeloma (MM) is the second most common hematologic malignancy characterized by clonal proliferation of abnormal plasma cells in the bone marrow. In the United States (US), an estimated 34,920 new cases of MM were diagnosed in 2021 with 12,410 deaths estimated ([SEER-MM, 2021](#)).

The clinical outcome and survival of MM has been dramatically improved over the last decade with the wide use of proteasome inhibitors (PIs; eg, bortezomib, carfilzomib) and immunomodulatory imide drugs (IMiDs; thalidomide, lenalidomide, and pomalidomide) as standard of care ([Brenner et al., 2009](#); [Kumar et al., 2008](#); [Thumallapally et al., 2016](#)). However, the majority of MM patients will relapse after the initial treatment. Over the course of disease, after each line of therapy, the disease becomes more aggressive, and the duration of remission becomes progressively shorter. The median overall survival in MM patients who were PI- and IMiD-refractory was only 8 months ([Usmani et al., 2016](#)).

Daratumumab is a first-in-class anti-cluster of differentiation (CD)38 antibody approved for RRMM, which has shown an encouraging response rate in RRMM both as a single agent or in combinations with a PI and/or an IMiD ([Chari et al., 2017](#); [Dimopoulos et al., 2018](#); [Lonial et al., 2016](#); [Moreau et al., 2019](#); [Spencer et al., 2018](#)). Another anti-CD38 antibody, isatuximab, showed similar activities ([Attal et al., 2019](#); [Martin et al., 2015](#); [Richter et al., 2016](#)) and was approved for RRMM in combinations with a PI or an IMiD. Although the clinical efficacy of daratumumab is well established, there are about 60% of patients not responding to the treatment, and eventually all patients progress.

In addition to antibody treatment, there are multiple B-cell maturation antigen (BCMA) chimeric antigen receptor T cell (CAR-T) therapies currently in development for MM ([Gagelmann et al., 2020](#)). Although anti-tumor activity is very promising, the toxicity of cytokine release syndrome (CRS) can potentially be life-threatening.

In summary, MM remains as an incurable disease after multi-modality therapies. There is a significant unmet medical need for subjects with RRMM who have exhausted standard-of-care or are resistant to prior therapies.

##### 2.1.1.2 *Acute Myeloid Leukemia*

Acute myeloid leukemia (AML) is the most common type of leukemia in adults, accounting for 36% of all leukemias with a median age of 68 years at diagnosis. In the US, the estimated new cases of AML in 2021 is 20,240 with estimated deaths of 11,400. The 5-year survival rate (2011 to 2017) remains low at 29.5% ([SEER-AML, 2021](#)).

AML is characterized by accumulation of abnormal myeloid blasts in the bone marrow leading to bone marrow failure and dysfunctional hematopoiesis ([Lowenberg et al., 1999](#)). Although the majority of AML patients will achieve a remission after the initial treatment with the conventional chemotherapy (ie, a “7+3” regimen), approximately two-thirds of patients will relapse and require salvage therapies. If a patient fails to achieve remission (primary refractory)

or relapses afterwards, the prognosis is dismal, with a median survival of 6 to 9 months (Heuser et al., 2020).

In recent years, our understanding of genetic and epigenetic signatures of AML has significantly advanced. Multiple targeted therapies including FLT3 inhibitors, IDH1/2 inhibitors, and BCL2 inhibitors have shown encouraging results when combining with cytotoxic or hypomethylating agents (Kayser and Levis, 2018). However, for the vast majority of relapsed or refractory AML (R/R AML) patients, therapeutic options are limited with an unsatisfactory clinical outcome. Allogeneic hematopoietic stem cell transplant (HSCT) remains as the only potential cure for patients with intermediate risk and adverse risk disease. Novel therapies are needed to control the disease progression, induce deep and sustained remission, and potentially bridge patients to transplantation.

### **2.1.1.3 Diffuse Large B-Cell Lymphoma**

DLBCL is the most common aggressive lymphoma representing 30% to 35% of all non-Hodgkin lymphoma (NHL) cases (Ghielmini et al., 2013). Although the majority of DLBCL patients can be cured with combinational immuno-chemotherapy (ie, rituximab plus doxorubicin-based combination chemotherapy, R-CHOP), approximately one-third of patients will develop relapsed or refractory disease. It is known that DLBCL patients with high-risk features (eg, double-hit lymphoma, transformed lymphomas, or early relapse) will become refractory to standard therapies and will have limited alternatives for cure.

For patients with relapsed or refractory DLBCL (R/R DLBCL), approximately 60% remain sensitive to conventional second-line immunochemotherapy; and these patients can undergo subsequent high-dose chemotherapy (HDT) followed by autologous HSCT and achieve long-term survival (Gisselbrecht et al., 2010; Sehn et al., 2012b). On the contrary, R/R DLBCL patients who do not respond to second-line immunochemotherapy only have a life expectancy of 4 months (Elstrom et al., 2010; Friedberg, 2011; Van Den Neste et al., 2016). Due to advanced age and/or comorbidities only about half of R/R DLBCL patients are eligible for HDT-HSCT. For transplant-eligible candidates who have failed second-line therapy or whose disease has relapsed post-transplantation, the prognosis is dismal.

Recently, CD19-directed CAR-T cell therapies (ie, KYMRIA®, YESCARTA®, BREYANZI®) have revolutionized the treatment of refractory B-cell lymphoid malignancies and demonstrated durable remissions in R/R large B-cell lymphomas including DLBCL, high grade B-cell lymphoma (HGBCL), and primary mediastinal large B-cell lymphoma (PMBCL), and follicular lymphoma (Abramson et al., 2020; Locke et al., 2019; Schuster et al., 2019). However, potentially life-threatening toxicities including CRS and neurotoxicity, extended production time precluding patients with rapidly progressing disease, and high-treatment expense have limited the access. Additional immunotherapies including ZYNLONTA® (Caimi et al., 2021), MONJUVI® (Duell et al., 2021; Salles et al., 2020), and POLIVY® (Sehn et al., 2020; Sehn et al., 2022) and a targeted agent XPOVIO® (Kalakonda et al., 2020) have demonstrated encouraging activity in R/R DLBCL either as monotherapy or in combinations although these are unlikely to be curative.

Taken together, most R/R DLBCL patients cannot expect to be cured with secondary therapies and a new investigational therapy with manageable toxicities is needed.

### **2.1.2 Introduction to GEN3014**

GEN3014 (also referred to as HexaBody®-CD38 or IgG1-**CC1**-028-E430G) is a human immunoglobulin (Ig)G1κ monoclonal antibody (mAb) that contains the hexamerization-

enhancing mutation E430G (HexaBody technology, Genmab) and binds with high affinity to an epitope on human CD38.

HexaBody molecules are regular IgG1 antibodies that have an engineered fragment crystallizable (Fc)-region containing a single mutation, such as E430G, that enhances the formation of ordered hexameric structures upon binding to membrane-expressed antigens through Fc-Fc interactions between monomeric IgG molecules (de Jong et al., 2016). The hexameric antibody structures form the optimal docking site for the hexavalent complement component C1q, which is the first component of the classical pathway of complement activation (Diebolder et al., 2014; Ugurlar et al., 2018). Consequently, introduction of a hexamerization-enhancing mutation has been shown to result in enhanced complement-dependent cytotoxicity (CDC) activity for antibodies against different hematological cancer targets, such as CD20, CD52 and CD38. HexaBody molecules are monomeric in solution, and only upon cell surface antigen binding, antibody hexamerization occurs (de Jong et al., 2016).

HexaBody-CD38 is designed to induce strong anti-tumor activity in CD38-expressing tumors through highly potent CDC and other Fc-mediated effector functions, including antibody-dependent cellular cytotoxicity (ADCC) and antibody-dependent cellular phagocytosis (ADCP). In addition to these direct anti-tumor activities, by the depletion of CD38-expressing cells (and thereby CD38 enzyme activity) as well as direct inhibition of CD38 cyclase activity, GEN3014 might also cause a relief of immune suppression in the tumor microenvironment and result in potentiation of anti-tumor immune responses.

